We propose to test BUP microdosing vs. treatment as usual (TAU), meaning standard BUP induction. We will conduct a hybrid type 1 effectiveness-implementation study, using a pragmatic, open-label, randomized controlled trial (RCT). We will randomize 270 hospitalized patients with (a) CP and (b) opioid misuse or OUD to a 4-day microdosing protocol (without stopping full agonists) or 2-day standard induction (with stopping full agonists), and link them to outpatient BUP treatment. Study assessment visits will occur at baseline, 1 week, and 1, 3, and 6 months. The primary outcome will be BUP treatment uptake (taking BUP 7 days after baseline). Secondary OUD outcomes will be illicit opioid use and retention in care at 1, 3, and 6 months. Secondary pain outcomes will be pain intensity, pain interference, and quality of life at 3 months. Changes in pain and quality of life will be mediated by BUP treatment uptake and retention. During induction and 3-months of follow-up, we will also collect data for Ecological Momentary Assessment (EMA) of opioid withdrawal, craving, pain, and anxiety ("opioid- and pain-related symptoms"). These EMA data will allow us to assess whether BUP microdosing's targets of engagement—opioid- and pain-related symptoms—mediate OUD outcomes. Exploratory analyses will also examine pain as a trigger for opioid relapse.

Aim 1: To test the effectiveness of microdosing (vs. TAU) on OUD outcomes.

***H₁:* The microdosing arm (vs. TAU) will have better BUP treatment uptake and retention, and less illicit opioid use. *H₂:* Improvements in H₁ will be mediated by opioid- and pain-related symptoms.**

Aim 2: To test the effectiveness of microdosing (vs. TAU) on pain outcomes.

***H₃:* The microdosing arm (vs. TAU) will have less pain intensity and interference, and improved quality of life. *H₄:* Improvements in H₃ will be mediated by OUD outcomes.**

Aim 3: To inform future implementation and dissemination efforts, we will: 3a) Examine factors influencing reach, adoption, implementation, and maintenance of BUP microdosing. We will use qualitative and quantitative methods to describe multi-level factors influencing these domains; **3b) Calculate**

the cost and examine cost-effectiveness of BUP microdosing. H_5 : Compared with TAU, BUP microdosing will be cost-effective from a societal and a health sector perspective.

[figure not shown]
B. SIGNIFICANCE

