B.3 Fear of withdrawal prevents people from initiating BUP. Needing to transition to BUP from opioid agonists (i.e. heroin or prescription opioids) prevents people with opioid misuse or OUD from starting BUP. There are two challenges: 1) patients must typically avoid opioids for 24-72 hours before starting BUP; and 2) *precipitated or persistent withdrawal* during BUP induction can lead to early treatment cessation. If BUP is taken too soon after full opioid agonists, opioid-dependent people will experience precipitated withdrawal when BUP displaces other opioids at mu opioid receptors while providing only partial agonism. Relative reduction in opioid agonist activity is experienced as withdrawal,^{44,50,51} which can reduce interest in BUP treatment.^{52,53} People taking prescribed opioids express fear of stopping opioids due to worsening pain and withdrawal.^{9,10,54-57} Two early studies that attempted to transition patients with CP and likely OUD from prescription opioids to BUP highlight induction challenges. In one trial, 21 patients consented to transition from prescription opioids to BUP, but only 12 took BUP and 4 successfully completed induction.⁵⁸ In a retrospective pain clinic study, only 104 of 271 patients receiving prescription opioids who were offered BUP successfully transitioned to BUP.⁸ One study of 76 CP patients with opioid misuse used an inpatient protocol to transition to BUP; the protocol included conversion to intravenous opioids and giving small doses of intramuscular or sublingual BUP.⁵⁹ This worked, but elective hospitalization for BUP induction is too resource intensive to be generalizable. Even when BUP induction is successful, as many as 28% of patients drop-out during the first week of treatment, likely due to

Figure E-1. Study summary

uncontrolled craving and withdrawal.⁶⁰⁻⁶⁴ Improved BUP induction protocols are needed.

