D.2.1 Overview of study approach: We will conduct a hybrid type 1 effectiveness-implementation study, using a pragmatic, open label RCT. We will recruit 270 hospitalized patients with (a) CP and (b) opioid misuse or OUD, randomize them 1:1 to BUP microdosing or TAU, and link them to outpatient BUP treatment. We will assess BUP treatment uptake (primary outcome) and other OUD and pain outcomes. The microdosing arm will use a 5-day BUP microdosing protocol (see **Figure E-2** and **Table E-2**) – BUP doses will be gradually increased while a full opioid agonist is continued. In the TAU arm, participants will stop other opioids and wait until they are in moderate opioid withdrawal before starting BUP. Both arms will receive follow-up care at Montefiore clinics to continue BUP treatment (with buprenorphine-naloxone) and manage CP. Assessment visits will occur at baseline, 1 week, and 1, 3, and 6-months. We will use EMA to assess opioid- and pain-related symptoms during induction and three 1-week periods over 3 months. We will also collect detailed information on microdosing implementation and cost-effectiveness.

D.2.2 Setting. We briefly describe study sites below and details are provided in the Facilities section. Montefiore Medical Center is the largest healthcare provider in The Bronx. The neighborhoods served by Montefiore are representative of low-income urban areas: over 65% of patients have public insurance, 57% Hispanic and 39% Non-Hispanic Black, and neighborhoods have been devastated by drug use. There are three Montefiore hospitals in the Bronx. Hospitalized medical patients are typically cared for by hospitalists with the availability of pain, addiction medicine, and psychiatry consultants. Montefiore also has 20 community health centers, the BUP Treatment Network (situated in 7 community clinics), and 5 opioid treatment programs. In outpatient settings, patients receive BUP treatment integrated with primary care services.

D.2.3 Participant Eligibility: We will enroll hospitalized patients with CP and opioid misuse or OUD who are taking opioids and eligible for BUP treatment. Opioid misuse will be defined as heroin use or prescription opioid misuse (defined as: 1) use without a prescription; 2) use in greater amounts, or more often than prescribed 3) running out of prescription pain medication early).¹⁰⁷ CP will be defined as pain that is chronic

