(on most or all days for ≥ 3 months) and at least moderate intensity and interference (score ≥ 4 on Pain, Enjoyment of Life and General Activity scale [PEG]).^{108,109} We will exclude patients who are currently receiving any OUD treatment (see **Table E-1**).

Table E-1: Inclusion and Exclusion Criteria

Inclusion Criteria	Exclusion Criteria

 • Age ≥ 18 years • Opioid misuse or OUD (see D.2.3) • Chronic pain (see D.2.3) • Currently taking opioids • Fluency in English or Spanish • Planned hospitalization for ≥ 48 hours 	
 • Current OUD treatment (BUP, methadone, naltrexone) • Severe alcohol or benzodiazepine use disorder • Hypersensitivity to BUP or naloxone • Pain due to malignancy • Severe untreated mental illness (suicidality, psychosis) • presence of an acute or chronic medical condition that would make participation medically hazardous • Resting respiratory rate >20 or O₂ saturation $<92\%$ • Pregnancy • Unable to consent due to pain or cognitive impairment

D.2.4 Recruitment:

We will actively and passively recruit hospitalized patients. Clinicians in the hospital, including pain and addiction consultants, will be informed about the study. Study information will be posted electronically and in common areas (e.g., physicians' lounges). [name], Director of Montefiore's Addiction Consult Service, and [name], Director of the Pain Service, will oversee recruitment of patients on whom they are consulted. Hospital Medical Directors will also assist in recruitment. We will also have the Epidemiology Informatic Unit (EISMU) produce daily recruitment data lists with identifiable information about hospitalized patients who have opioid use disorder and at least one chronic pain condition. We will contact the attending physician for hospitalized patients before approaching the patient for study recruitment. If given permission by the attending physician, the research coordinator will approach the hospitalized patient for recruitment.

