3	Full dose	2 mg q8	6 mg	--	8 mg BID	16 mg
4	Full dose	4 mg q8	12 mg	--	8 mg BID	16 mg

D.2.7 Clinical Protocols: Microdosing**(Experimental arm):**

Participants randomized to microdosing will start low-dose BUP while continuing a full opioid agonist according to a 4-day protocol (see **Figure E-2 & Table E-2**). Participants will be assessed for opioid withdrawal using the clinical opioid withdrawal scale (COWS) before the first BUP dose and 30 minutes after each administered dose while hospitalized.¹¹¹ A full opioid agonist will be continued until day 5 of the protocol.^{112,113} If patients are planned for discharge before completing

microdosing, they will receive at the time of discharge pre-packed medication clearly marked with the timing for each dose, instructions on how to take the medication and when to stop full agonist opioids. Opioid withdrawal will be assessed with the Subjective Opioid Withdrawal Scale (SOWS) via telephone.

Rationale for 5-day protocol: Published microdosing protocols range from 3 to 7 days or more. From 2012-2016, the mean length of stay for patients at Montefiore Medical Center with an opioid positive urine drug test was 7.62 days (95% CI: 7.44-7.80). Some evidence suggests that rapid titration to maintenance BUP treatment dosages prevents drop-out,¹¹⁴ but rapid titration could increase precipitated withdrawal risk, therefore, we developed our protocol in the middle of the published range.

TAU (Control arm): Participants randomized to TAU will receive a standard BUP induction following clinical guidelines. Full opioid agonists will be stopped and a clinician will assess for withdrawal using the COWS scale. If participants have a COWS score of ≥ 8 they will be eligible to receive a 2 mg BUP dose. Participants will be reassessed for withdrawal 30 minutes after receiving their first BUP dose.

Withdrawal management: Participants with COWS score increases of $\geq 50\%$ or an absolute increase of 4 or more will be considered to have precipitated withdrawal. If this occurs, induction will be postponed to the following day. Clinicians can administer non-opioid adjunctive medications (i.e., clonidine, loperamide) during induction based on hospital protocols. Medication use will be considered a covariate in analyses with withdrawal symptoms as an outcome.

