Table E-7 outlines the cost categories we will take into account when assessing incremental costs in each of the two reference case perspectives. We excluded cost categories not relevant to the timeframe of this study (e.g., impact on educational achievements). Because buprenorphine microdosing will occur during the index hospitalization only, we will not consider costs of patient time attending the intervention. The research team will have access to health insurance claims data for 40-50% of patients to be enrolled because their health plans make claims available to Montefiore for care management and research. For health care service costs, in addition to patient self-reports using validated questionnaires (see above) we will conduct a secondary analysis with these patients using the claims data, which are not subject to recall biases and not prone to missing data.

Table E-7. Cost components for the two reference case perspectives				
Cost Category	Health Care	Societal	Source(s) of Data	Unit Cost/Monetary Conversion Factor
Costs of intervention delivery	Yes	Yes	Medical records, micro-induction-protocol, and length of stay in hospital for the index hospitalization	Cost per night of hospital stay
Costs of other health care services	Yes	Yes	Non-Study Resources Form (see D.4.1)	Various sources ¹⁴⁴ (e.g., Medicare/ Medicaid data, Kaiser Family Foundation)
Productivity – labor market earnings	No	Yes	Self-reports (see D.4.1)	Hourly wage rates reported at research interviews

Criminal Justice involvement	No	Yes	Criminal Activities Form (see D.4.1)	Unit societal cost estimates for various types of crime ¹⁴⁵
------------------------------	----	-----	--------------------------------------	--

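### The cost analysis assumes microdosing happens only in hospital although D.2.7 lets it finish at home, and discharge before a first TAU dose has no stated rule

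*Combined protocol and SAP*

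**What the plan says.** **Eligibility.** Table E-1 requires "Planned hospitalization for ≥ 48 hours". It gives no starting point: admission, consent and randomisation are all possible readings.

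**Microdosing schedule.** The Specific Aims and D.2.7 describe a 4-day protocol. D.2.1 says "The microdosing arm will use a 5-day BUP microdosing protocol", B.9 and the rationale in D.2.7 also say 5 days, and D.2.7 adds "A full opioid agonist will be continued until day 5 of the protocol". Table E-2 lists four days.

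**TAU schedule.** The Specific Aims call it a 2-day standard induction, and Table E-2 schedules the first BUP on day 2. D.2.7 makes the first dose depend on a COWS score of at least 8 and, in either arm, postpones induction by a day after precipitated withdrawal. B.3 says of standard inductions that "patients must typically avoid opioids for 24-72 hours before starting BUP".

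**Early discharge.** The microdosing paragraph of D.2.7 has a provision opening "If patients are planned for discharge before completing": pre-packed timed doses, instructions, and SOWS by telephone. The TAU paragraph has no counterpart. The paragraph on follow-up treatment gives all participants a 1-week BUP supply and a clinic visit within a week.

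**Primary outcome.** E.2.10 defines uptake as receiving BUP 7 days after baseline, from EHR records of hospital administration or prescription.

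**Costs.** D.4.1 reasons "Because buprenorphine microdosing will occur during the index hospitalization only" and on that basis leaves out patient time. For intervention delivery, Table E-7 lists medical records, the micro-induction protocol and index length of stay as sources, with a hospital night as the unit cost.

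**The concern.** Two parts of the plan cannot both be true. D.2.7 expects some participants to complete microdosing after discharge, while D.4.1 rests a costing rule on that never happening. If the rule stands, the resources used to finish microdosing at home (dispensed supply, calls, patient time) may drop out of the incremental cost that H5 tests.

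The stay criterion makes this more than a rare event in principle, because it admits people whose planned stay is shorter than the microdosing schedule. The same criterion exposes a gap in TAU: a participant may be discharged before reaching the withdrawal threshold for a first dose, and the plan says neither what follows nor how that person is scored at day 7. These participants remain in the intention-to-treat comparison, so the primary contrast would partly depend on an unwritten rule.

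**Working it through.** The plan gives no figure for how many participants will leave before completing induction, so there is none to reproduce. The check compares its stated durations, doses and costing rules. Hour 0 is taken as the start of induction day 1.

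**1. Stay against microdosing schedule.** 4 days = 4 × 24 = 96 hours; 5 days = 5 × 24 = 120 hours. The 48-hour minimum covers 48/96 = 50% or 48/120 = 40%.

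**2. Microdosing doses by 48 hours (Table E-2).**

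| Day | Doses | mg |
|---|---|---|
| 1 | 2 × 0.5 | 1 |
| 2 | 3 × 1 | 3 |
| 3 | 3 × 2 | 6 |
| 4 | 3 × 4 | 12 |

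Total: 2 + 3 + 3 + 3 = 11 doses and 1 + 3 + 6 + 12 = 22 mg. By 48 hours: 2 + 3 = 5 doses and 1 + 3 = 4 mg. If the 48 hours run from admission and some have elapsed, less will have been given.

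**3. Stay against TAU.** The 2-day label equals 2 × 24 = 48 hours, and Table E-2 schedules 8 mg on day 2. On schedule, therefore, TAU fits a 48-hour stay as far as first doses are concerned. It may not fit when the COWS threshold is reached late (the 72-hour end of the wait in B.3 exceeds 48) or when induction is postponed a day. The 16 mg that D.2.7 sets as the discharge target first appears for TAU on day 3, after hour 48.

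**4. Costing passages side by side.**

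| Item | D.2.7 | D.4.1 and Table E-7 |
|---|---|---|
| Place of microdosing | Hospital, or completed after discharge | Index hospitalization only |
| Patient time | Used when dosing at home | Not considered |
| Pre-packed supply | Issued at early discharge | No unit cost listed |
| Telephone SOWS | Done after discharge | No unit cost listed |

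D.2.7 attaches these items to microdosing alone, so leaving them out can only lower that arm's cost. For scale, B.9 cites $37,029 to $47,480 per hospitalization over 5.74 to 5.82 days: 37,029/5.82 ≈ $6,362 and 47,480/5.74 ≈ $8,272 per day. A few doses and calls are probably small beside that, but the ratio uses the difference between arms, which the documents do not give.

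**5. Direction of any effect on uptake.** Let q be the share of TAU discharged before a first dose (an assumption; the documents give no value) and p the uptake they would otherwise have had. Scoring them all as failures costs TAU p × q. Scoring them all as uptake because a supply was prescribed adds (1 − p) × q. D.2.12 gives 24% for TAU; 61%, its microdosing rate, serves as a high case.

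| q | p = 24%: all fail | p = 24%: all count | p = 61%: all fail | p = 61%: all count |
|---|---|---|---|---|
| 5% | −1.2 points | +3.8 | −3.1 | +2.0 |
| 10% | −2.4 | +7.6 | −6.1 | +3.9 |
| 20% | −4.8 | +15.2 | −12.2 | +7.8 |

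The sign depends wholly on the scoring rule. Take-home microdoses raise the same question: if supply alone counts, microdosing also gains (1 − 0.61) × its own early-discharge share.

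**The case against.** The case for leaving the plan alone is substantial. Forty-eight hours is a minimum, and D.2.7 cites a mean stay of 7.62 days. Early discharge from microdosing is foreseen and provided for. TAU is labelled 2-day and scheduled to reach 8 mg by hour 48, against 4 mg for microdosing. The 24-72 hour wait is background text; the trial's own trigger is the COWS score. The 1-week supply covers both arms. In a pragmatic trial, being able to finish at home may be part of the strategy under test. On costs, the stated exclusion is patient time only, and clinicians log the time they spend on induction (D.2.9).

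Most of this stands, and it limits the point. It does not remove the contradiction between D.2.7 and D.4.1, supply a start for the 48 hours, or say what happens to, and how to score, a TAU participant discharged before a first dose.

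Two stronger readings are tempting and unsupported.

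- A reader might assume an exponential remaining stay with mean 5.62 to 7.62 days, find 12-16% leaving between 48 and 72 hours, multiply by 61%, and infer that microdosing is flattered by 7-10 points. The 7.62 days describes patients with an opioid-positive urine test in 2012-2016, not enrolled participants from randomisation. An exponential stay is memoryless, so 2 elapsed days do not cut its mean to 5.62. TAU can lose only the uptake it would have had: at 24%, 0.24 × 12% to 0.24 × 16%, or about 3 to 4 points. Even that assumes every such participant fails, although dosing is scheduled from day 2 and a discharge supply may count as uptake.
- A reader might infer that home-completed microdosing is costed at zero. Table E-7 also lists medical records and the micro-induction protocol as sources, so this is not shown.

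**Conclusion.** The contradiction between D.2.7 and D.4.1 is certain from the text. Its consequence is that post-discharge delivery costs specific to microdosing may be left out of the cost-effectiveness ratio. The direction favours microdosing; the size is unknown and probably small.

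The planned stay has no start point and is shorter than the microdosing schedule under either stated duration. For TAU it matches the nominal 2 days but not a delayed first dose. Because no rule covers TAU discharge before a first dose, and a discharge supply might count as uptake, day-7 uptake could be distorted in either direction. The share affected cannot be computed from the documents, and the figures in the last table of the working are illustrations resting on an assumed share. The documents do not support a claim that the primary comparison is biased toward microdosing by any stated amount. No sample-size figure changes.

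**What to change.** 1. In D.4.1 and Table E-7, delete the premise that microdosing is confined to the index stay. Add post-discharge induction supply, telephone contacts and patient time to intervention delivery costs in both arms, using dispensing and call records.
2. In Table E-1, state that the 48 hours are counted from randomisation.
3. Reconcile Table E-1, Table E-2 and D.2.7 (including its follow-up paragraph) on discharge before induction is complete in each arm, and reconcile the 4-day and 5-day descriptions. The clinical content is for the sponsor to decide.
4. In E.2.10, state whether BUP supplied at discharge to a participant who has not started, or not completed, induction counts as uptake. Settle this before outcome data are examined by arm.
5. Record whether induction was completed in hospital or after discharge, and report this descriptively by arm. It should not define subgroups for the primary outcome, because it is determined after randomisation and differs between arms by design.

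The cost is protocol wording, one recorded item and a few cost lines, drawn largely from records the trial should already generate. Patient time may need a short question or a stated assumption. Counting the 48 hours from randomisation may exclude a few patients close to discharge; the costing correction has no effect on recruitment.

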Our multidisciplinary team will test a *BUP microdosing protocol where patients start very low doses of BUP without stopping other full opioid agonists*. We hypothesize that microdosing will increase BUP uptake by (1) avoiding the 24-72 hour period of withdrawal required for standard inductions and (2) reducing the risk of precipitating withdrawal.¹³ BUP binds mu opioid receptors with higher affinity than other opioids but provides only partial agonism. Therefore, if full agonists occupy mu opioid receptors when patients take normal BUP doses, they will experience the relative reduction in agonism as "precipitated" withdrawal. During standard inductions, patients avoid displacing full agonists by waiting to take BUP until they are in moderate opioid withdrawal. BUP "microdoses" do not displace enough full agonist to precipitate withdrawal; therefore, patients can start and gradually increase BUP doses without stopping other opioids. Case studies suggest that BUP microdosing is feasible and minimizes withdrawal,¹⁴ but no clinical trials have established safety and efficacy.¹⁵

Targeting hospitalized patients will allow us to reach people at high-risk for opioid-related harms who are not already connected to outpatient care.¹⁶ Hospitalization is a critical "touchpoint" that often precedes opioid overdose.¹⁷ Even when pain consultants are available, they rarely have experience managing both CP and opioid misuse or OUD. Evidence supports starting BUP during hospitalization to increase linkage to outpatient OUD treatment,^{18,19} but microdosing could change clinical practice by improving BUP treatment uptake. Our premise is that microdosing will improve long-term pain outcomes and reduce unnecessary hospitalizations specifically by facilitating initiation of BUP treatment in a non-treatment-seeking population.

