D.3.4 Qualitative data collection: [name] (early-stage investigator) or an RA will conduct 45-60 minute semi-structured interviews with participants and hospital providers. We will sample 20-30 participants in the microdosing arm, including those who do and do not initiate BUP. Participant interviews will occur after BUP induction. We will also interview 10 hospital providers who care for study participants. After completing interviews, if new themes continue to emerge, we will randomly select additional participants until thematic saturation is achieved. Patient interviews: We will develop a semi-structured interview guide with input from people with lived experience that asks open-ended questions about patients' experiences with induction, particularly acceptability and reasons for BUP initiation or lack of initiation, and whether BUP helps with pain. Provider interviews will elicit information about factors associated with achieving RE-AIM outcomes (reach, effectiveness, adoption, implementation, and maintenance). The interview guide will be informed by CFIR domains regarding implementation of induction and referral procedures at the hospitals. Using the 5 CFIR domains, we will probe how various factors enable or hinder implementing the microdosing protocol. This includes ease of initiating BUP (e.g., feasibility), inner organization (e.g., fit and acceptability within hospitals), outer setting (e.g., social factors influencing clinical practice), perceptions of individuals involved (e.g., BUP

Table E-6: Aim 3a Implementation Measures

Construct	Quantitative Measures	Qualitative Assessment
Reach	# and % of pts with CP and OUD screened # and % of pts with CP and OUD enrolled # and % of pts with CP and OUD ineligible Rates of enrollment at each hospital	Log of verbatim reasons patients stated for declining enrollment
Adoption	# and % of participants assessed for induction # and % of participant completing induction # and % of participants referred for outpatient BUP treatment # and % of participants linked to outpatient BUP treatment	Interviews with participants about their experience, including barriers and facilitators to treatment initiation and linkage
Implementation	# and % of participants who receive ≥ 1 dose of BUP within assigned induction protocol Intervention fidelity check-list	Interviews with providers about barriers and facilitators to implementation

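### Table E-2, TAU day 2: 2 mg every 4 hours comes to 12 mg over a day, not the stated 8 mg, and no cap or dosing window reconciles the two

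*Combined protocol and SAP*

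**What the plan says.** Table E-2 (placed between D.2.6 and D.2.7) gives, for each arm and day, the BUP dose with its frequency and a daily total. Its Standard Induction half reads:

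- day 1: full agonist stopped, no BUP;
- day 2: 2 mg every 4 hours, total 8 mg;
- days 3 and 4: 8 mg twice daily, total 16 mg.

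D.2.7 supplies the text for the arm: "Participants randomized to TAU will receive a standard BUP induction following clinical guidelines". Full agonists are stopped, withdrawal is scored, and of those with a COWS score of at least 8 it says that "they will be eligible to receive a 2 mg BUP dose". Withdrawal is reassessed 30 minutes after that first dose. D.2.1 gives the same condition in words: TAU participants "wait until they are in moderate opioid withdrawal before starting BUP". For precipitated withdrawal, D.2.7 adds "If this occurs, induction will be postponed to the following day".

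Neither the table nor the text states a maximum number of doses, a maximum first-day dose, or a dosing window for TAU day 2. Nor do they say what happens if the COWS score is already 8 or more on day 1, or still below 8 on day 2.

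**The concern.** The frequency and the daily total sit in the same row and imply different amounts of drug. An order written from the frequency allows 12 mg on the first BUP day; one written from the total stops at 8 mg. This is the control arm of a trial whose question is how BUP is started, so the first-day dose is part of the treatment under comparison. D.2.7 itself treats titration speed as relevant: its rationale for the microdosing schedule notes that faster titration may prevent drop-out but could raise the risk of precipitated withdrawal.

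What is at stake is uniform delivery of TAU and a clear description of it in the report. The documents give no basis for a direction or size of effect on uptake.

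**Working it through.** **Inputs.** Dose, interval and stated daily total for each dosed row of Table E-2.

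**Formula.** Daily total = dose × 24 / interval in hours, with twice daily taken as every 12 hours.

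| Row | Calculation | Result | Stated |
|---|---|---|---|
| Microdosing day 1 | 0.5 × 24/12 | 1 mg | 1 mg |
| Microdosing day 2 | 1 × 24/8 | 3 mg | 3 mg |
| Microdosing day 3 | 2 × 24/8 | 6 mg | 6 mg |
| Microdosing day 4 | 4 × 24/8 | 12 mg | 12 mg |
| TAU day 2 | 2 × 24/4 | **12 mg** | **8 mg** |
| TAU day 3 | 8 × 24/12 | 16 mg | 16 mg |
| TAU day 4 | 8 × 24/12 | 16 mg | 16 mg |

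Six of seven rows reproduce, so the table counts a full 24 hours. TAU day 2 does not reproduce: the gap is 12 − 8 = 4 mg, and 4/8 = 50% of the stated total.

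**Can 8 mg be recovered?** 8 mg is 8/2 = 4 doses. At 4-hour spacing these fall at 0, 4, 8 and 12 hours. Counting doses from time 0 up to, but not including, the end of a dosing window:

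- 10 to 12 hours: 3 doses, 6 mg;
- 14 to 16 hours: 4 doses, 8 mg;
- 18 to 20 hours: 5 doses, 10 mg;
- 22 to 24 hours: 6 doses, 12 mg.

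So 8 mg is consistent with a shortened first day, or with an unstated cap of four doses. A 6-hour interval also gives it: 2 × 24/6 = 8 mg.

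**Where the figure is used.** The primary outcome (section on key outcomes for Aims 1 and 2) is receipt of BUP 7 days after baseline, yes or no. The sample size (D.2.12) uses uptake proportions of 61% and 24%. The primary implementation measure (D.3.3) needs at least one BUP dose on the induction day. None of these takes a daily total as input.

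**The case against.** The strongest defence is that the row is a shorthand. TAU dosing begins only once withdrawal has appeared, so the first BUP day may well be short, and four doses is a plausible intention. On that reading the row lacks a cap and is not wrong in substance. This stands as an explanation of how the row may have arisen. It does not settle what the row instructs, because the available text does not state the cap and every other row counts a full day. Figure E-2, the order set and the induction check-list are not in the available text and may already resolve it.

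Several stronger readings are tempting, and the documents do not support them.

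- *That the COWS condition contradicts the day-2 row.* The score makes a participant eligible, and the table can be read as the nominal schedule. The postponement rule shows that calendar days are expected to move. No text orders a day-2 dose regardless of score. What remains is a small omission: no rule for an early or late start.
- *That the 24-72 hour wait conflicts with the table.* That text is background on standard inductions in general (B.3: "patients must typically avoid opioids for 24-72 hours before starting BUP"), not a TAU instruction, and stopping on day 1 with dosing on day 2 fits its lower end.
- *That the two-day description in the Specific Aims conflicts with reaching 16 mg on day 3.* A stop day plus a first-dose day is two days. D.2.7 makes 16 mg the target at discharge for both arms, and the four-day microdosing schedule itself ends at 12 mg.
- *That fidelity in TAU cannot be scored.* Table E-6 counts participants with at least one "dose of BUP within assigned induction protocol", which is the same at 8 or 12 mg. All administered doses are recorded and a check-list is used; its content is not shown, so its adequacy cannot be judged either way.

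**Conclusion.** The TAU day-2 row of Table E-2 is internally inconsistent. As written, the frequency gives 12 mg over 24 hours against a stated 8 mg. This is a 4 mg (50%) ambiguity in a first-day opioid dose, and the only mismatch among seven dosed rows. The conclusion assumes that the frequency applies around the clock, as in the other six rows, and that no cap exists in material not shown.

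The point is small but real. A reader might infer that the comparator is undefined or the primary result biased; neither follows. The core of TAU is stated: stop the agonist, wait for a COWS score of at least 8, start at 2 mg, aim for 16 mg. On either reading of the row, the next scheduled day is 16 mg. A reader might also infer that all 135 TAU participants are affected, but the discrepancy reaches only those who start BUP. In the trial cited for the TAU uptake assumption, 12 of 21 consenting patients took any (B.3).

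**What to change.** Make the row agree with itself. The simplest change keeps the stated 8 mg: *2 mg every 4 hours, maximum 4 doses (8 mg) on the first BUP day*, or alternatively *2 mg every 6 hours*. If 12 mg is what the investigators intend, correct the daily total instead. The choice is clinical; the statistical requirement is that one amount is stated. Then check the order set and the induction check-list against the chosen wording.

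As a minor accompanying clarification, label the TAU BUP days in Table E-2 as counted from the first COWS score of 8 or more. An early start (day 1) or a late one (after day 2) is then handled in the same way for every participant.

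The cost is a few words in the protocol and a check of two working documents. No new data, participants or analyses are needed.
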